7.6. Description of Subgroups to be Analyzed

Subgroup analyses for the primary endpoint will be performed by the stratification variable for randomization, as well as by important variables for baseline demographics and patient characteristics. These analyses are for the RW period only. Details will be provided in the SAP.

7.7. Statistical Analysis Methodology

This Section outlines the overall methodologies. Details of the statistical analyses, methods, and data conventions will be described in the SAP.

7.7.1. General Methods

Statistical analysis will be performed using SAS[®] software Version 9.4 or later. Continuous variables will be summarized using the mean, the standard deviation, median, minimum value, and maximum value. Time-to-event variables will be summarized using percent censored, event rate, and 25th, 50th, and 75th percentiles with 95% CI, if estimable.

Categorical variables will be summarized using frequency counts and percentages. Data will be listed in data listings.

At each of RI and RW periods and in the LTE, baseline will be the last value before the first dose of study drug within each individual period unless otherwise specified. For change-over-time endpoints in the RW period, by-visit analysis will be performed at each scheduled visit for at least 24 weeks.

The analysis for treatment comparison will be triggered after at least the 22nd CEC-confirmed pericarditis recurrence events have been accrued. At that time, randomization will be closed, and subjects will return to study sites for the EORW visit. At that point study treatment will stop (completing the database for the primary efficacy endpoint analysis), and subjects will either continue into the LTE or complete their study participation. Missing data due to end of RW period will be considered as missing at random. Handling of missing values will be described in the SAP.

7.7.2. Stratified Analysis

There will be 2 stratification variables for randomization:

- Oral CS use at RI baseline: yes or no
- Diagnosis of recurrent idiopathic pericarditis at RI baseline: yes or no

When a stratified analysis is used in the analysis and a stratum has no event of interest or no responder, the stratum will be pooled with the other stratum in the same stratification variable.

7.7.3. Testing Hypotheses and Multiplicity Adjustment

All statistical tests for the treatment comparison of efficacy endpoints in the RW period will be based on the ITT analysis set with 1-sided $\alpha=0.025$ unless otherwise specified. For each endpoint, the null hypothesis is that the effects of rilonacept and placebo are the same. The alternative hypothesis is that rilonacept is better than the placebo.

In order to control the overall 1-sided type I error rate at the 0.025 level, a gatekeeping procedure in combination with Hochberg's procedure will be applied to testing the primary and major secondary endpoints. If the 1-sided p-value for testing the primary endpoint is ≤ 0.025 , a significant treatment effect on the primary endpoint will be claimed.

Section 7.2.1 provides the order of major secondary endpoints. If the primary endpoint is significant, the first major secondary endpoint, i.e., proportion of subjects who maintained Clinical Response at Week 24 of RW period will be tested at 1-sided $\alpha=0.025$. A significant treatment effect on this major secondary endpoint will be claimed if the 1-sided p-value is ≤ 0.025 . If the treatment effect is not significant on the primary endpoint, significance on this major secondary endpoint cannot be claimed regardless of the result.

If both primary and first major secondary endpoints are significant following the above procedure, the second and third major secondary endpoints defined in Section 7.2.1 will be tested with Hochberg's procedure at overall 1-sided $\alpha=0.025$. If both 1-sided unadjusted

p-values are ≤ 0.025 , claim significance of rilonacept for both endpoints. If the larger 1-sided p-value is > 0.025 , compare the smaller 1-sided p-value with 0.0125. If the smaller 1-sided p-value is ≤ 0.0125 , claim significance of rilonacept on this endpoint.

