7.2.1. Major Secondary Efficacy Endpoints

- Proportion of subjects who maintained Clinical Response at Week 16 of the RW period. Clinical Response is defined as a weekly average of daily pericarditis pain on the 11-point NRS ≤ 2.0 and CRP level ≤ 0.5 mg/dL, and on monotherapy of randomized study drug at Week 16.
- Percentage of days with no or minimal pain in the first 16 weeks of the RW period. No or minimal pain is defined as non-missing NRS ≤ 2 .
- Proportion of subjects with absent or minimal pericarditis symptoms (based on the 7-point PGIPS) at Week 16 of the RW period.

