7.2.2. Other Secondary Endpoints

All time-to-event endpoints start from the day of randomization. The following variables will be analyzed:

- Proportion of subjects who maintained Clinical Response at Week 8 and Week 24 of the RW period, respectively
- Percentage of days with no or minimal pain (pain ≤ 2 on the 11-point NRS) in the first 8 weeks and 24 weeks of the RW period, respectively
- Proportions of subjects with absent or minimal pericarditis symptoms (based on the 7 point rating scale of PGIPS) at Week 8 and Week 24 of the RW period, respectively
- Proportion of subjects without pericarditis recurrence in the first 24 weeks of the RW period
- Time to pericarditis pain NRS ≥ 4
- Time to CRP level ≥ 1 mg/dL. This is for elevation of CRP for which no other cause other than pericarditis was identified.
- Time to pericardial rub
- Time to widespread ST-segment elevation or PR-segment depression on ECG, whichever occurs first
- Time to new or worsening pericardial effusion on ECHO
- Change in category of ECHO pericardial effusion size at week 24 and end of RW based on central labs
- Change over time in CRP levels
- Change over time in the subject's assessments of pericarditis pain (weekly average)
- Proportion of subjects with absent or minimal pericarditis activity based on the PGA-PA over time

- Proportion of subjects with absent or minimal pericarditis activity over time based on the PGIPS over time
- Change over time in SF-36 Physical and Mental Component Scores and domain scores (Physical Functioning, Role-Physical, Bodily Pain, General Health, Vitality, Social Functioning, Role-Emotional, and Mental Health domains)
- Changes in SF-6D, 6 domain scores and utility index
- Change in EQ-5D-5L. There are 6 questions in this instrument (Section 6.2.1.8). Each of the first 5 questions has 5 levels, from level 1 (best) to level 5 (worst). They are mobility, self-care, usual activities, pain/discomfort, and anxiety/depression. The sixth question is the health on the day, from 0 (the worst) to 100 (the best) (van Reenen and Janssen 2015). The levels of the first 5 questions (EQ-5D-5L profile) will be converted to an index value. Change from baseline in each one of these 7 values will be an endpoint.
- Change in subject's sleep quality assessed with the ISI (Section 6.2.1.9). There are 7 items in the ISI. Change in ISI total score, which is the sum of the 7 items over time, will be the endpoint.

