7.7.5. Analysis of Secondary Efficacy Endpoints

7.7.5.1. Analysis of the Major Secondary Endpoints

The analyses for the 3 major secondary endpoints will be based on the ITT Week 16 analysis set, with the Week 8 and Week 24 ITT analysis sets providing supportive sensitivity analyses.

- Proportion of subjects who maintained Clinical Response at Week 16 of the RW period (defined as a weekly average of daily pericarditis pain ≤ 2.0 on the 11-point NRS, CRP ≤ 0.5 mg/dL, and on monotherapy of randomized study drug at Week 24). The Cochran–Mantel–Haenszel (CMH) test will be used in this analysis, stratified by the stratification variables for randomization.
- Percentage of days with no or minimal pain in the first 16 weeks post randomization. Minimal or no pain is defined as non-missing daily NRS ≤ 2 on the 11-point NRS. This endpoint will be analyzed with an analysis of covariance. In addition to treatment arm, the following covariates will be included in this analysis: the stratification variables for randomization, and RI baseline NRS weekly average in 2 categories: NRS ≤ 2 versus NRS > 2 .
- Proportion of subjects with absent or minimal pericarditis symptoms (based on the 7-point PGIPS) at Week 16 of the RW period. The CMH test will be used in this analysis, stratified by the stratification variables for randomization.

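### Section 7.7.3 tests the gatekeeping secondary endpoint at Week 24, while the endpoint section it cites places that endpoint at Week 16

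*Protocol*

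**What the plan says.** All places are in Protocol Version 3.0 (Amendment 2), the current text.

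- **Section 7.7.3** sets the procedure "In order to control the overall 1-sided type I error rate at the 0.025 level". It states that "Section 7.2.1 provides the order of major secondary endpoints", and then names the first of them: the "proportion of subjects who maintained Clinical Response at Week 24 of RW period will be tested at 1-sided" level 0.025. Only if that test succeeds are the second and third endpoints tested, by Hochberg's procedure.
- **Section 7.2.1**, first item: "Proportion of subjects who maintained Clinical Response at Week 16 of the RW period". The response definition ends "and on monotherapy of randomized study drug at Week 16". The synopsis also gives Week 16.
- **Section 7.2.2** lists among the other secondary endpoints: "Proportion of subjects who maintained Clinical Response at Week 8 and Week 24 of the RW period, respectively".
- **Section 7.7.5.1**: "The analyses for the 3 major secondary endpoints will be based on the ITT Week 16 analysis set", with Week 8 and Week 24 as supportive. Its first bullet is headed Week 16, but the definition in parentheses ends "and on monotherapy of randomized study drug at Week 24".
- **Section 7.5** assigns endpoints measured at Week 16 to subjects randomized at least 16 weeks before data cutoff, and endpoints measured at Week 24 to those randomized at least 24 weeks before.

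**The concern.** The paragraph that allocates alpha contradicts the section it cites. Week 16 and Week 24 Clinical Response are different hypotheses and, under Section 7.5, belong to different analysis sets. Section 7.7.5.1 adds a third version, a Week 16 endpoint with one component read at Week 24.

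The endpoint is the gate to two further confirmatory claims. If its time point is not settled before unblinding, it could be chosen with results in view. The sets may also differ a good deal in size, because Version 3.0 closes the randomized withdrawal period on events and drops the 24-week minimum follow-up.

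**Working it through.** **1. The plan's own figure.** Section 7.4 gives HR 0.244, 1-sided 2.5%, power 90% and 1:1 allocation. Events = (1.960 + 1.282)² / (0.25 × (ln 0.244)²) = 21.1, rounded up to 22; power at 22 events is 91.1%. The stated 22 is reproduced, and nothing below alters it.

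**2. The places side by side.**

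| Place | Time point of first major secondary | Monotherapy judged at |
|---|---|---|
| Synopsis | Week 16 | not stated in that item |
| 7.2.1 | Week 16 | Week 16 |
| 7.7.5.1 | Week 16, ITT Week 16 set | Week 24 |
| 7.7.3 | Week 24 | not stated |
| 7.2.2 | lists Week 24 as other secondary | not stated |

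Version 2.0 used Week 24 in its Sections 7.2.1, 7.7.3 and 7.7.5.1. The simplest explanation is that two phrases were missed when the endpoint moved to Week 16.

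**3. Type I error at this step.** One fixed test, at either week, has error 0.025. If the more favourable of two tests could be taken, the error is 1 − Φ₂(1.960, 1.960; ρ), where ρ is the correlation of the two statistics. The protocol does not give ρ, so a range is shown:

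- ρ = 0: 1 − 0.975² = 0.0494
- ρ = 0.5: 0.045
- ρ = 0.7: 0.042
- ρ = 0.8: 0.039
- ρ = 0.9: 0.035

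Every ITT Week 24 subject is also in the ITT Week 16 set, so positive correlation is expected and the first value is an upper bound.

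**4. Size of the two sets.** I simulated exponential recurrence (placebo median 8 weeks, HR 0.244) with the cutoff at event 22, 4,000 runs per scenario. Numbers randomizable and accrual time are assumptions, with uniform entry. Median Week 16 / Week 24 set sizes:

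- 50 subjects over 26 weeks: 20 / 4
- 50 over 52: 25 / 17
- 90 over 39: 17 / 0
- 90 over 52: 21 / 7
- 90 over 78: 24 / 15

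**5. Power at the gate.** Assume that response equals no recurrence and that the CMH test is unstratified (the protocol stratifies it). The placebo rate is 0.5^(t/8), which is 0.25 at Week 16 and 0.125 at Week 24. The rilonacept rate is that value to the power 0.244, which is 0.713 and 0.602. Enumerating all outcomes, with rejection at z ≥ 1.960:

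- Week 16: 8 per arm 47%, 9 per arm 45%, 10 per arm 54%, 11 per arm 63%, 12 per arm 70%
- Week 24: 2 per arm 0%, 4 per arm 33%, 8 per arm 55%

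At equal size Week 24 is no weaker (8 per arm: 55% against 47%). The loss comes from the smaller set.

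**6. The mixed definition in 7.7.5.1.** A subject randomized 16 to 24 weeks before cutoff is in the ITT Week 16 set but has no Week 24 assessment in the period. Response requires all components, so anyone who has already failed one is a non-responder regardless. In the five scenarios 57% to 59% of subjects in that window had recurred by cutoff (for example 8.8 of 15.1 on average with 50 over 26 weeks). If recurrence ends randomized monotherapy, status is undetermined only for those still responding.

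**The case against.** The strongest reply is that the protocol largely answers the question itself. Section 7.7.3 defers to Section 7.2.1 for the order, Section 7.7.5.1 names the ITT Week 16 set and calls Week 24 supportive, and Section 7.2.2 keeps Week 24 outside the controlled family. The statistical analysis plan, not available here, may say so outright. This stands as evidence of intent: the two readings are not equally supported. It does not remove the defect, because the alpha-allocating sentence names Week 24 expressly and must be overridden by inference.

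Three stronger inferences are tempting, and the documents do not support them.

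- A reader might infer that strong type I error control is lost. It is not lost under either reading alone; it fails only if the choice is made with results in view.
- A reader might infer that the mixed definition cannot be computed for anyone randomized 16 to 24 weeks before cutoff. It can be for those who have already failed a component.
- A reader might set a single Week 16 power of 63% against a lower Week 24 range. That figure holds only at 11 per arm; on the same assumptions the Week 16 range is 45% to 70%, and it overlaps the Week 24 range.

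**Conclusion.** The contradiction is real and lies in the current text; it is not a difference from an amendment log. Section 7.7.3 names the wrong time point for an alpha-carrying hypothesis, and Section 7.7.5.1 carries a second Week 24 remnant that leaves status undetermined for subjects randomized 16 to 24 weeks before cutoff who are still responding. Week 16 is very probably what is meant.

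Error control at this step is not guaranteed while the choice stays open. The exposure is about 0.035 to 0.049 instead of 0.025, depending on an assumed correlation. Under assumed accrual of 50 to 90 subjects over 26 to 78 weeks, the median set is about 17 to 25 at Week 16 and 0 to 17 at Week 24. Power is then about 45% to 70% (8 to 12 per arm) and 0% to 55% (0 to 8 per arm), if response equals no recurrence and the test is unstratified. These figures show that the time point could decide whether the gate opens; they are not forecasts. The finding itself rests on the text.

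**What to change.** Before unblinding, by protocol clarification:

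- In Section 7.7.3, change Week 24 to Week 16 for the first major secondary endpoint and name the ITT Week 16 analysis set there, since that section otherwise defaults to the full ITT set.
- In the first bullet of Section 7.7.5.1, change the monotherapy time point to Week 16, to match Section 7.2.1.
- Keep Week 8 and Week 24 Clinical Response as supportive, and carry the same wording into the statistical analysis plan.

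The cost is two wording changes plus the named set. There is no added data collection or patient burden, and no change to the primary endpoint, its alpha, the 22 events or the sample size.

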7.7.4. Analysis of Primary Efficacy Endpoint

Primary analysis of this study will be triggered after at least the 22nd CEC-confirmed pericarditis recurrence events have been accrued. The log rank test will be the primary method for the analysis of time to recurrence, stratified by the stratification variables for randomization. Detailed censoring rules will be described in the SAP.

A sensitivity analysis will be performed based on the Investigator's judgement of pericarditis recurrence. Additional sensitivity analyses may be defined in the SAP.

7.7.5. Analysis of Secondary Efficacy Endpoints

7.7.5.1. Analysis of the Major Secondary Endpoints

The analyses for the 3 major secondary endpoints will be based on the ITT Week 16 analysis set, with the Week 8 and Week 24 ITT analysis sets providing supportive sensitivity analyses.

- Proportion of subjects who maintained Clinical Response at Week 16 of the RW period (defined as a weekly average of daily pericarditis pain ≤ 2.0 on the 11-point NRS, CRP ≤ 0.5 mg/dL, and on monotherapy of randomized study drug at Week 24). The Cochran–Mantel–Haenszel (CMH) test will be used in this analysis, stratified by the stratification variables for randomization.
- Percentage of days with no or minimal pain in the first 16 weeks post randomization. Minimal or no pain is defined as non-missing daily NRS ≤ 2 on the 11-point NRS. This endpoint will be analyzed with an analysis of covariance. In addition to treatment arm, the following covariates will be included in this analysis: the stratification variables for randomization, and RI baseline NRS weekly average in 2 categories: NRS ≤ 2 versus NRS > 2 .
- Proportion of subjects with absent or minimal pericarditis symptoms (based on the 7-point PGIPS) at Week 16 of the RW period. The CMH test will be used in this analysis, stratified by the stratification variables for randomization.

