6.1.3. Randomization (RI Week 12/RW Baseline Visit)

All procedures for the RI Week 12 visit should be performed prior to randomization in IWRS. Subjects who stopped background SOC pericarditis therapy and who achieve Clinical Response (see Section 6.2.2) at RI Week 12 visit will be randomized in the IWRS and will complete the procedures for the RW Baseline visit. If randomization has been closed, subjects achieving Clinical Response after completing the RI period may transition directly to the LTE.

For subjects that do not qualify for randomization, the Sponsor or [REDACTED] medical monitor is to be immediately contacted to evaluate the reasons for non-qualification. Following medical monitor consultation, if the subject is deemed to not be a treatment responder, study drug will be discontinued, and the subject will not proceed to randomization. The subject will complete the EOT visit and continue with follow-up according to the SOA until the end of the RW period. Refer to Section 13.1 for a comprehensive list of procedures in the Schedule of Activities for this visit.

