6.2.1.10. Cardiac Magnetic Resonance Imaging

Cardiac MRI will be performed as described in Section 13.1 in subjects at selected sites in the cardiac MRI substudy. Cardiac MRI will be performed to assess any changes in pericardial inflammation. Cardiac MRI readings will be performed by a central imaging laboratory. The study site/clinic reading of the MRI at the time of the examination may be used by the Investigator for clinical decision-making.

6.2.2. Assessment of Clinical Response at the End of the Run-In Period Week 12/RW Baseline

At RI Week 12/RW baseline visit, all subjects receiving rilonacept who are able to discontinue background SOC pericarditis therapy during the RI period (Section 3.1) are assessed for Clinical Response. Only subjects who achieve Clinical Response at RI Week 12 and have discontinued background medications for pericarditis are eligible for randomization in the RW period.

Clinical Response at RI Week 12 is defined as follows:

- A weekly average of daily pericarditis pain of ≤ 2.0 on the 11-point NRS during the 7 days prior to and including the day of randomization, **AND**
- CRP level ≤ 0.5 mg/dL at the RI Week 12/RW baseline visit.

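### The Week 16 PGIPS test is valid but leaves out RW-baseline PGIPS, which could cost about 2 to 8 points of power if that baseline varies and is strongly prognostic, and roughly nothing otherwise

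*Protocol*

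**What the plan says.** All references are to Protocol Version 3.0 (Amendment 2).

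- **Endpoint (Section 7.2.1).** The third major secondary endpoint is: "Proportion of subjects with absent or minimal pericarditis symptoms (based on the 7-point PGIPS) at Week 16 of the RW period".
- **Test (Section 7.7.5.1).** "The CMH test will be used in this analysis, stratified by the stratification variables for randomization". Section 7.7.2 lists two such variables: oral corticosteroid use at RI baseline, and "Diagnosis of recurrent idiopathic pericarditis at RI baseline: yes or no". Neither measures symptoms, and both precede randomization by 12 weeks.
- **Alpha (Section 7.7.3).** The endpoint belongs to the controlled family. It is tested by Hochberg's procedure with the pain-days endpoint at one-sided 0.025. If the larger p-value fails, the instruction is to "compare the smaller 1-sided p-value with 0.0125".
- **Entry to the RW period (Section 6.2.2).** "Only subjects who achieve Clinical Response at RI Week 12 and have discontinued background medications for pericarditis are eligible for randomization". Clinical Response there means mean weekly pain of at most 2.0 and CRP of at most 0.5 mg/dL. PGIPS is not a condition.
- **Collection.** Table 2 in Section 13.1 schedules PGIPS at RI Week 12/RW baseline, and Section 6.1.3 states: "All procedures for the RI Week 12 visit should be performed prior to randomization in IWRS".
- **Analysis set (Section 7.5).** The test uses subjects randomized at least 16 weeks before data cutoff. The size of this set is not stated.

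**The concern.** The endpoint is a status at Week 16, not a change. PGIPS rates overall symptoms at the time of asking, and Section 6.2.1.5 defines mild as symptoms that can be ignored with effort. A subject with mean pain of 2 could reasonably choose that category. Such a subject meets the randomization criteria but already counts as a non-responder on this endpoint.

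Baseline status on the same scale may predict Week 16 status. If it does, leaving it out leaves explainable variation in the comparison. The value is a true pre-randomization covariate and needs no extra visit. What is at stake is efficiency on an alpha-controlled endpoint, which may be judged at 0.0125, in an analysis set that may be smaller than the number randomized. Because Section 7.7.5.1 fixes the test, the point concerns something the protocol states and not a detail left to the SAP.

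**Working it through.** **1. The plan's own figure.** Section 7.4 gives hazard ratio 0.244, one-sided 2.5%, 90% power and 22 events.

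- Schoenfeld events: 4 × (1.960 + 1.282)² / (ln 0.244)² = 42.03 / 1.990 = 21.1, rounded up to 22.
- Enrolment: 50 / 0.90 = 55.6, rounded up to 56.

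Both reproduce. The protocol gives no response rate, baseline distribution or power for PGIPS, so every PGIPS input below is an assumption.

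**2. Strong association, planned CMH against additive adjustment.** Assumed Week 16 response, rilonacept and placebo: 85% and 45% if absent or minimal at RW baseline, 30% and 10% if worse. The implied baseline odds ratios are:

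- rilonacept: (0.85/0.15) / (0.30/0.70) = 13.2
- placebo: (0.45/0.55) / (0.10/0.90) = 7.4

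Simulation used 5,000 trials per setting, allocation stratified on the two factors, and one-sided 0.025. N is assumed. The protocol plans 50 randomized, and the Week 16 set may be smaller.

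| N | Worse than minimal at RW baseline | Planned CMH | Additive, with baseline PGIPS | Gain (points) |
|---|---|---|---|---|
| 26 | 20% | 44.0% | 50.2% | 6.2 |
| 40 | 10% | 70.0% | 75.5% | 5.5 |
| 40 | 20% | 64.4% | 71.5% | 7.1 |
| 50 | 20% | 73.6% | 80.3% | 6.7 |

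Over N of 26 to 50 and 5% to 20% worse than minimal, the gain runs from about 2 to about 8 points, with the low end at 5%. Type I error with the baseline term was 2.4% to 2.6%.

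**3. Varying the association.** The same additive test was run without and with baseline PGIPS, which isolates the covariate. Settings: N = 50, marginal response 40% and 75%, 4,000 trials each. Cells show power without, then with, the covariate.

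| Worse than minimal | OR 1 | OR 3 | OR 10 |
|---|---|---|---|
| 5% | 72.9 → 72.5 | 72.9 → 72.4 | 73.1 → 74.2 |
| 10% | 72.1 → 70.9 | 72.6 → 72.8 | 72.5 → 74.8 |
| 20% | 73.2 → 72.3 | 73.3 → 74.1 | 73.6 → 78.9 |
| 30% | 71.8 → 70.9 | 72.6 → 72.8 | 72.2 → 80.6 |

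At OR 1 the term costs 0.4 to 1.2 points. At OR 3 the change is −0.5 to +0.8. Here, gains of 5 points or more need at least 20% worse than minimal and an odds ratio near 10.

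**4. Headroom.** Section 7.4's placebo median of 8 weeks implies a Week 16 recurrence-free rate of 0.5^(16/8) = 25% on placebo and 0.25^0.244 = 71% on rilonacept. If PGIPS response followed these rates, power at N = 50 would already be about 92%, rising to 93% to 96% at OR 10.

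**5. How to adjust.**

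- *Extra CMH stratum.* This turns four strata into eight. At N = 50 with 40% and 75%, power falls by 0.6 to 1.4 points at OR 3. In smaller sets with a weak association the loss reaches about 4 to 5 points.
- *Maximum-likelihood logistic regression.* With share q worse than minimal, the chance that none of them responds is (1 − 0.3q)^(N/2) × (1 − 0.1q)^(N/2) under the rates in step 2. For N = 40, q = 20% this is 0.94^20 × 0.98^20 = 19%. For N = 40, q = 10% it is 0.97^20 × 0.99^20 = 44%. For N = 26, q = 20% it is 0.94^13 × 0.98^13 = 34%. In those cases the baseline coefficient has no finite estimate.

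**The case against.** The strongest case against is that nothing here is wrong. The CMH test follows the randomization factors, as the stratified log-rank test does, and it holds its type I error. The protocol reports neither how PGIPS is distributed at RW baseline nor how well it predicts Week 16. Randomized subjects have low pain, CRP of at most 0.5 mg/dL and no background therapy apart from opioids that could not be stopped, so ratings worse than minimal may be rare. A nearly constant covariate removes little noise.

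Most of this stands. It rules out three stronger readings that a reader might infer:

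- *That the omission does lower power.* The documents cannot show this. It holds only if the baseline varies and is strongly prognostic.
- *That an imbalance of two or three baseline non-responders makes the test misleading.* Randomization makes such imbalances part of the error the test already allows for. Adjustment affects precision, not validity.
- *That the plan contradicts itself because Section 7.7.5.2 adjusts other endpoints for baseline.* Those are change-from-baseline models, whereas the responder endpoints use CMH.

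What the objection does not remove is the asymmetry. The data are already collected, the possible loss from adjusting is about a point, and the possible gain is several points.

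**Conclusion.** The point holds as a conditional efficiency improvement, not as an error. The planned test is valid and may stay in the plan. If 5% to 20% of randomized subjects are worse than minimal at RW baseline and the baseline odds ratio is about 7 to 13, the planned CMH gives up about 2 to 8 points of power against an additive adjusted analysis (N of 26 to 50, one-sided 0.025). With an odds ratio of about 3 or less, or almost everyone absent or minimal at randomization, the difference is roughly nil, within about 1.5 points either way. The rates, the association and the size of the Week 16 set are all assumptions. The documents establish only the omission, the timing of collection and the absence of a PGIPS entry condition.

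**What to change.** Before unblinding, prespecify for PGIPS at Week 16 an additive analysis with treatment, the two randomization factors and RW-baseline PGIPS (absent or minimal versus worse). Report the adjusted risk difference and its test, and state that this p-value enters the Hochberg step. Use a method that stays estimable with sparse cells, for example a linear-probability or residual-based test, or Firth-penalized logistic regression with standardization. Do not add baseline PGIPS as a further CMH stratum. Keep the planned CMH as supportive.

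The blinded pooled distribution of RW-baseline PGIPS can be checked first. If nearly all subjects are absent or minimal, there is little to gain.

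The cost is analysis wording and one more model term in a small sample, at most about 1 to 1.5 points of power if baseline PGIPS is not prognostic. No new data or visits are needed.
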